Title: Otoacoustic Emission Suppression Study

Number: NCT04749524

Document Date: 08/15/2024

**Project Funded by NIH NIDCD SBIR Grant R44-DC018491-01A to
Intelligent Hearing Systems Corp.**

Grant Title:

Optimized Medial Olivocochlear Reflex Screening and Testing Module

Study Protocol and Statistical Analysis Plan

Study Protocol:

Objective:

The objective of this study is to develop an optimized hearing testing method using otoacoustic emissions (OAE), that can be used to efficiently assess peripheral neural function (including retrocochlear disorders) using the medial olivocochlear reflex (MOCR). This reflex has been shown to be abnormal in patients with neural disorders. The focus of this project will be the development of a screening method that incorporates OAE screening and measurement of the MOCR in the same test procedure. The target population in the proposed research is infants, particularly those in environments where auditory brainstem response (ABR) screening is not performed routinely. Addition of the MOCR to screening where ABR is not performed will address the shortcoming of OAE screening which misses neural forms of hearing loss.

Design:

The study uses an observational Case-Control design comparing the MOCR measures of individuals with normal hearing with those with hearing loss in a typical clinical recording environment. MOCR measurements were conducted in one session.

Methods:

The testing procedure is explained to the subjects, or their parents, and they are asked to sign an Informed Consent Form approved by the Vanderbilt University Medical Center Institutional Review Board.

A small rubber or foam tip is placed in the entrance of the ear canal during all tests. The tip is connected to earphones for behavioral hearing testing, or a middle ear muscle reflex or OAE measurement probe.

Adult and child subjects are first tested using behavioral hearing techniques to determine hearing thresholds and middle ear muscle reflexes. Behavioral hearing testing requires a subject to indicate if they hear sound tones being presented. The subject is asked to raise their hand or push a button when they hear tones delivered through earphones. Sound tones are varied in intensity and frequency to determine the subject's audiogram.

For the middle ear muscle reflex testing and OAE testing, the subject will be asked to sit quietly while sounds are played into their ears. Middle ear muscle reflexes use an ear probe to present a sound tone and measure changes in the sound pressure level of the tone caused by middle ear muscle contractions associated with the presentation of a loud ipsilateral (same ear) or contralateral (opposite ear) sound.

All subjects were tested with the OAE MOCR technique. During OAE MOCR testing, sounds are presented to the ear and a very sensitive microphone in a probe measures very tiny sounds generated by the ear in response to the sounds presented.

Measurements are conducted in one session lasting less than two hours. Adult and child subjects are given the option of watching a silent movie during the test. Infant subjects are typically tested during natural sleep.

Statistical Analysis Plan (SAP):

MOCR strength data was analyzed across defined spectral bands using a special version of the IHS Smart TrOAE module. Frequency domain data are obtained using fast Fourier transforms (FFT). Like conditions (i.e., without elicitor; with elicitor) were compared for data consistency within subjects to quantify variability. Following individual quantification, data will be compared across subjects. Subjects with noisy OAEs (physiological or ambient acoustical noise) will be excluded from the final analysis.

Planned statistical procedures for the above experiments included analysis of variance and t-tests to determine the effects of the testing factors on the dependent variables (MOCR strength, noise, sweeps and test time). A linear mixed effects model, grouping the data by each of the testing factors and levels, will be used to develop a regression model between the various factors and dependent variables. Distributions from the infant data will provide preliminary information to consider related to sensitivity and specificity. The proposed MOCR methods will be compared to TEOAE and ABR newborn screening information.

Informed Consent Form and IRB Approvals (2019-2022):

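### Does the SAP need changing because no analysis names the normal-hearing versus hearing-loss contrast, or age group as a factor?

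*Combined protocol and SAP*

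**What the plan says.** The Design section sets one between-subject question: a case-control study "comparing the MOCR measures of individuals with normal hearing with those with hearing loss". The Methods describe three kinds of subject. Adults and children have behavioural audiometry first and may watch a silent film during testing. Infants are usually asleep, and no behavioural thresholds are described for them. The Objective makes infants the target population.

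The first SAP paragraph analyses MOCR strength by spectral band and then makes a within-subject check: "Like conditions (i.e., without elicitor; with elicitor) were compared for data consistency within subjects to quantify variability". It goes on: "Following individual quantification, data will be compared across subjects".

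The second SAP paragraph plans ANOVA and t-tests "to determine the effects of the testing factors on the dependent variables", which it lists as MOCR strength, noise, sweeps and test time. It adds a linear mixed effects model, "grouping the data by each of the testing factors and levels", "to develop a regression model between the various factors and dependent variables". Infants appear in a strand of their own: "Distributions from the infant data will provide preliminary information to consider related to sensitivity and specificity". A comparison of methods closes the plan: "The proposed MOCR methods will be compared to TEOAE and ABR newborn screening information".

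**The concern.** The SAP names its outcomes but not its explanatory variables. The only condition with stated levels is the elicitor, and that is compared within subjects. A reader who looks for the analysis that answers the Design question does not find it labelled. Factors that act on sweeps and test time also read more naturally as recording conditions than as hearing status.

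Age makes the silence look more serious. Age and test state go together, since infants sleep while older subjects may watch a film. If hearing-loss subjects differed in age from those with normal hearing, and age shifted MOCR strength, an unadjusted contrast would mix the two effects. The text permits both an age-pooled and a within-age analysis, so the choice could be made after seeing the data. It also does not say how infants are classed by hearing status, or whether they enter the contrast.

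**Working it through.** The documents give no sample size, alpha, effect size, SD or age mix, so there is no figure of the plan's to reproduce. The check is textual, followed by an illustration on assumed values.

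**1. SAP statements set against the Design contrast**

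| SAP statement | Names hearing status? | Names age group as a factor? | Could carry the contrast? |
|---|---|---|---|
| Analysis by spectral band | No | No | Yes, as the outcome |
| Elicitor consistency check | No | No | No, it is within subject |
| Comparison across subjects | No | No | Yes |
| ANOVA and t-tests | No | No | Yes |
| Linear mixed effects model | No | No | Yes, with age and repeated measures |
| Infant distributions | No | No, a separate data set | Not in that form |
| Comparison with newborn screening | No | No | No, it compares methods |

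A whole-word count over the two SAP paragraphs (164 words) agrees: hearing 0, loss 0, normal 0, age 0; infant 1, newborn 1, elicitor 2, factors 3. So the contrast is unnamed, while the methods able to estimate it are present. Infants are mentioned, but only in their own descriptive strand and through newborn screening.

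**2. Can the gap be filled from the document itself?** For adults and children, hearing status comes from the behavioural tests in Methods. The contrast comes from Design. The between-subject step is the comparison across subjects, and the mixed model is the natural place for a hearing-status term. For infants, the TEOAE and ABR newborn screening information is a plausible source of classification, though the SAP does not state that link.

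**3. What would be at stake if age were ignored?** Assume two age strata, a within-age SD of 1, a shift of d between strata, and the same hearing effect Δ in both. With age shares p1 and p0 in the two hearing groups:

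- unadjusted difference = Δ + d × (p1 − p0), so the gap from the within-age estimate is d × dp, where dp = p1 − p0;
- d = 0, or dp = 0, or only one age group in the contrast: gap 0;
- d = 0.5, dp = 0.2: 0.5 × 0.2 = 0.10 SD;
- d = 0.8, dp = 0.6: 0.8 × 0.6 = 0.48 SD.

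The formula depends on the common-effect assumption. With equal age mix but assumed effects of 0 and 0.8 SD in two equal strata, the pooled estimate is (0 + 0.8)/2 = 0.4, which matches neither stratum. Even equal age mix therefore does not make every pooled and within-age answer agree.

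**4. What would stratifying cost?** Assume 30 per hearing group and age shares of 0.5 ± dp/2. The unadjusted SE is √(2(1 + d²p(1 − p))/30). The stratified SE is √((1/a + 1/b)/2), where a and b are the two groups' counts within a stratum.

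- d = 0.5, dp = 0.2 (18 v 12): unadjusted √(2 × 1.06/30) = 0.2658; stratified √((1/18 + 1/12)/2) = 0.2635; ratio 0.991.
- d = 0.8, dp = 0.6 (24 v 6): unadjusted √(2 × 1.1024/30) = 0.2711; stratified √((1/24 + 1/6)/2) = 0.3227; ratio 1.19.
- One stratum alone at 6 v 24: 95% half-width 2.048 × √(1/6 + 1/24) = 2.048 × 0.4564 = 0.93 SD, on 30 people.

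Where the age mix differs little, stratifying costs nothing but there is little bias to remove. Where it differs a great deal, stratifying removes more bias at a visible price in precision.

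**The case for a change.** The best case for a change is that the document calls itself a statistical analysis plan and that what it leaves out is the design's own comparison, not a fine point. Comparing data across subjects names no groups. Saying that the mixed model could hold hearing status is not saying that it does. Pre-specification is worth having without proof of bias, and naming the terms would cost a few lines.

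Part of this stands. The link from Design to analysis is left to inference, the testing factors are unlisted, and infant classification is not described.

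The rest does not carry a change. Confounding by age is possible but not shown: nothing says that hearing-loss subjects occur in more than one age group, or that age shifts MOCR strength. If infants serve only their own strand, the remaining strata are children and adults, for whom the documents describe no procedural difference. Insisting that ages be combined only by stratification is one analyst's preference, because an age term in the planned model already deals with additive age differences. Age-specific contrasts would need a hearing-by-age interaction or separate models, with intervals as wide as the single-stratum figure suggests. Finally, the SAP reports some of its analysis in the past tense, so terms added now would be post hoc and could not recover pre-specification for work already done.

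**Conclusion.** The omission is real but calls for no change. The SAP is terse about its explanatory variables, while its planned methods suit the Design question and the Design sentence says which groups are to be compared. A competent analyst would enter hearing status as the between-subject term, consider age alongside it, and keep the infant strand as preliminary description. Nothing in the documents points to a different or wrong analysis.

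The effect on any result cannot be computed from the documents. The range of 0 to 0.48 SD rests wholly on assumed age shifts, age shares and a common hearing effect, and its upper end is an assumed extreme. The SE ratios of 0.99 and 1.19 also assume 30 per group. This conclusion would weaken if enrolment showed a marked age imbalance between hearing groups and the reported contrast ignored age. That would be a question about the analysis as carried out, which the plan as written neither requires nor rules out.

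### Does the SAP need a middle ear reflex check on MOCR strength, given that reflexes are measured in adults and children but never used in the analysis?

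*Combined protocol and SAP*

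**What the plan says.** In the protocol's Methods section, "Adult and child subjects are first tested using behavioral hearing techniques to determine hearing thresholds and middle ear muscle reflexes". The reflex test presents a tone through an ear probe to "measure changes in the sound pressure level of the tone caused by middle ear muscle contractions", these being "associated with the presentation of a loud ipsilateral (same ear) or contralateral (opposite ear) sound". In the MOCR test, "a very sensitive microphone in a probe measures very tiny sounds generated by the ear". No reflex test is described for infants, who are the target population.

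The Design section gives the main contrast: "The study uses an observational Case-Control design comparing the MOCR measures of individuals with normal hearing with those with hearing loss".

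In the SAP, "MOCR strength data was analyzed across defined spectral bands" by a special version of the manufacturer's software module. The within-subject check is that "Like conditions (i.e., without elicitor; with elicitor) were compared for data consistency within subjects to quantify variability". The only stated exclusion is that "Subjects with noisy OAEs (physiological or ambient acoustical noise) will be excluded from the final analysis". The dependent variables are MOCR strength and three others, covering noise, sweep count and duration. The testing factors in the mixed model are not listed. Reflex results do not appear in the SAP as an outcome, named factor, covariate, exclusion, subgroup or sensitivity analysis.

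**The concern.** By the protocol's own account, a loud sound in either ear can contract the middle ear muscles and alter a level read at a probe in the ear canal. The MOCR test reads a probe microphone with and without an elicitor sound. If the elicitor is loud enough to trigger the middle ear reflex in some ears, part of the change credited to the olivocochlear system might arise in the middle ear.

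At stake is the comparison of normal-hearing with hearing-loss subjects. If reflex activation differed between them, part of an observed difference, or part of a missing one, could have the wrong origin. The infant distributions that are to inform sensitivity and specificity would carry the same uncertainty. It looks odd to collect the reflex data in adults and children and then write no use for them.

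**Working it through.** The documents give no sample size, variance, elicitor level or reflex threshold, so there is no figure of the plan's to reproduce. The check sets the passages against each other and then looks at what a remedy would deliver.

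**1. Would the written safeguards reveal a middle ear component?** Assume, for illustration only, that MOCR strength is a simple difference in level. Write the recording without elicitor as A + e, and with elicitor as A − m − d + e′, where m is the olivocochlear effect, d a middle ear effect and e, e′ noise.

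- Repeats of the same condition: (A − m − d + e′₁) − (A − m − d + e′₂) = e′₁ − e′₂. The term d cancels, so a repeatable middle ear shift passes the consistency check.
- The noise exclusion acts on e and e′, not on d.
- The contrast between conditions estimates m + d. The hearing-group difference estimates (m₁ − m₀) + (d₁ − d₀).

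The safeguards are therefore blind to d. The bias in the group comparison is d₁ − d₀, which is zero if the reflex is not triggered or acts equally in both groups.

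**2. Which links in the chain to a wrong result are documented?**

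| Link needed | What the documents give |
|---|---|
| Elicitor reaches reflex threshold | Elicitor level, type and ear not stated; the reflex trigger is described only as loud |
| Contraction alters the emission measure | Stated only for the reflex test's own tone; the MOCR microphone is said to record sounds the ear itself produces |
| Activation differs by hearing group | Nothing stated |
| Nothing in the analysis handles it | Not known: the strength formula, the module's processing and the testing factors are not given |

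None of the four is established. The second link rests on both tests using a probe, which is an analogy and not a statement in the text.

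**3. Is there an ordinary reason for the reflex test?** It is done first, alongside hearing thresholds, before MOCR testing. That order fits describing or classifying subjects for a case-control comparison, and a test with that role need not reappear in the SAP. The documents do not confirm this reading.

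**4. What would a sensitivity analysis cost and deliver?** The natural candidate drops ears whose reflex threshold is at or below the elicitor level. All inputs here are assumptions: two ears per subject, between-ear correlation r of 0.3 to 0.7, and a fraction f of 0.1 to 0.3 of ears removed. A subject with both ears carries information 2/(1+r), and with one ear 1. With ears flagged at random, the variance ratio is

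V = [2/(1+r)] / [(1−f)² × 2/(1+r) + 2f(1−f)].

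- f = 0.1, r = 0.3: V = 1.5385 / (0.81 × 1.5385 + 0.18) = 1.079, so the standard error is multiplied by √V = 1.039. At r = 0.7 the factor is 1.019.
- f = 0.3: the factors are 1.145 (r = 0.3) and 1.087 (r = 0.7).
- Both ears always flagged together: 1/√(1−f) = 1.054 (f = 0.1) and 1.195 (f = 0.3), at any r.
- Only one of two equal groups affected: √((V+1)/2), which across both flagging patterns is 1.010 to 1.027 (f = 0.1) and 1.044 to 1.102 (f = 0.3).

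The precision loss is thus about 1% to 20%, and precision is not the obstacle. These figures describe the candidate analysis only and say nothing about the size of d.

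The obstacle is what the result would mean:

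- It needs per-ear reflex thresholds, on a scale comparable with the elicitor and for the matching ear. None of these is documented, nor is testing of both ears.
- If only presence or absence was recorded, the comparison would not show activation at the elicitor level.
- If the estimate changed, the cause could be removal of d or selection of ears related to hearing status.
- If it did not change, an approximate flag would not rule d out.
- Infants would not be covered, because no reflex test is described for them.

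**The case for a change.** The strongest case for a change is that the omission is plain, the main outcome has a possible alternative explanation, and both written safeguards miss it, as the algebra shows. Relevant data are already collected in adults and children. A labelled post hoc check would leave the main analysis untouched and need no new testing. Brevity of the document does not explain why a described measurement has no stated use, and an unlisted set of testing factors is no evidence that reflexes are among them.

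Much of this stands. The gap is real, the safeguards are blind to a consistent shift, and a reader cannot judge from the text whether a middle ear contribution has been ruled out. Two parts do not stand. First, it cannot be said that every change with the elicitor would be read as olivocochlear, because the documents do not state how the strength measure is computed or screened. Second, having data at hand does not make an analysis informative. The low cost is an argument for the check only if its answer could be interpreted, and on the documented information it could not.

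**Conclusion.** No change to the plan follows. The documents leave open whether a middle ear effect enters MOCR strength; they do not show that one occurred, and they allow no estimate of its size or direction. Bias in the group comparison would require both that the effect exists and that it differs between hearing groups, and neither is documented.

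What is missing is description: the elicitor's level, type and ear, whether reflex results served enrolment, description or analysis, and a note that infants have no described reflex test. A sensible analyst would supply these when reporting, and none alters a planned analysis. Excluding reflex-flagged ears is a debatable trade-off. Its cost in standard error is modest (about 1% to 20% under the assumed inputs), but its data requirements are undocumented and its answer ambiguous.

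This conclusion assumes that the reflex test served mainly to characterise subjects, which fits its place in the Methods but is not stated. If comparable per-ear thresholds exist, a count by hearing group of ears at or below the elicitor level would be useful description. The infant accuracy information is already called preliminary, which limits what could rest on it.

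### As written, the SAP drops subjects with noisy OAEs from the whole final analysis although noise is one of its dependent variables, so the noise analysis is selected on its own outcome

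*Combined protocol and SAP*

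**What the plan says.** The first paragraph of the Statistical Analysis Plan opens with the analysis of MOCR strength and the within-subject check of like conditions (with and without elicitor). It continues: "Following individual quantification, data will be compared across subjects". It then gives the exclusion rule: "Subjects with noisy OAEs (physiological or ambient acoustical noise) will be excluded from the final analysis". The unit removed is the subject, and the rule is not tied to any one outcome.

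The second paragraph plans analysis of variance and t-tests "to determine the effects of the testing factors on the dependent variables (MOCR strength, noise, sweeps and test time", followed by a linear mixed effects model relating the factors to the same dependent variables. The testing factors are not listed. No separate analysis set is given for noise, sweeps or test time, and no analysis that restores the excluded subjects is described.

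In the Study Protocol, the Design section describes a case-control study "comparing the MOCR measures of individuals with normal hearing with those with hearing loss in a typical clinical recording environment". The Objective section asks for a method "that can be used to efficiently assess peripheral neural function".

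**The concern.** Excluding unscorable recordings is ordinary practice when the outcome is a small signal such as MOCR strength. It is different when noise is itself the outcome: the rule then cuts off the upper part of the distribution that the analysis is meant to describe.

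The stake is practical. Noise, sweeps and test time are plausible measures of how efficient the method is. The rule expressly covers ambient noise, which is part of a typical clinical setting. If those recordings are removed before noise is summarised, noise can look lower than it was in use, and an effect of a testing factor on noise can be misestimated.

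**Working it through.** **Inputs.** The documents give no sample size, noise SD, noise limit or exclusion rate, so there is no stated figure to reproduce. Everything below is an assumption chosen to show a range. Noise is normal, in units of its SD (where SDs differ, in units of the smaller one), and subjects above a cut-off c are removed.

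**1. Mean noise, one group.** With a fraction q removed, c = z(1−q), and the mean falls by L = φ(c)/(1−q).

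| q | c | Fall in mean (SD) |
|---|---|---|
| 5% | 1.645 | 0.109 |
| 10% | 1.282 | 0.195 |
| 20% | 0.842 | 0.350 |

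If the judgement that a recording is noisy correlates only r with analysed noise, the fall is r × L. At r = 0.7 this is 0.7 × 0.109 = 0.08, 0.7 × 0.195 = 0.14 and 0.7 × 0.350 = 0.24 SD. At r = 0, or with no exclusions, there is no bias.

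**2. Between-group noise difference, if one is tested.** Take two equal groups with means 0 and 0.5, SD 1 in each, and one common cut-off chosen to remove q overall. The kept mean is m(μ) = μ − φ(c−μ)/Φ(c−μ).

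| q overall | c | Removed, quieter / noisier group | Observed difference (true 0.50) |
|---|---|---|---|
| 5% | 1.95 | 2.6% / 7.4% | 0.41 |
| 10% | 1.57 | 5.8% / 14.2% | 0.36 |
| 20% | 1.12 | 13.2% / 26.8% | 0.30 |

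At 10%, for example, m(0) = −0.123 and m(0.5) = 0.238, so the difference is 0.238 + 0.123 = 0.361. If the noise judgement correlates 0.8 or 0.5 with analysed noise, simulation gives 0.41 or 0.46 at 10% excluded.

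Shrinkage depends on similar spreads. With SD s, the kept mean is μ − s·φ(a)/Φ(a), where a = (c−μ)/s. At 10% excluded overall and a true difference of 0.50:

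- SD 1.5 in the quieter group and 1 in the noisier: 11.0% and 9.0% are removed, and the difference widens to 0.64.
- SD 1.3 and 1: 0.53, so almost no change.
- SD 1 and 1.5: 0.10, so severe shrinkage.

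**3. Within-subject contrast, such as with and without elicitor.** Assume between-subject variance 0.8, residual variance 0.2 and a true contrast of 0.50.

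- Exclusion on the subject's average noise leaves 0.50.
- Exclusion on the noisier condition alone moves that condition's mean by −L and the other's by −0.8L. The contrast is then 0.5 − 0.2L, which is 0.46 at 10% and 0.43 at 20%.
- Exclusion on the quieter condition alone gives 0.5 + 0.2L, which is 0.54 and 0.57.

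**4. Sweeps and test time.** The shift is again −r × L, but the sign of r is not known. For assumed r from −0.3 to 0.9 at 10% excluded, it runs from +0.3 × 0.195 = +0.06 to −0.9 × 0.195 = −0.18 SD.

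**The case against.** The strongest reply is that the rule is a data-quality rule for scoring OAEs. It stands in a paragraph that opens with MOCR strength, and it may never have been meant to govern the noise analysis. This is a fair reading, and for MOCR strength the rule is defensible. But the wording refers to the final analysis without restriction, and nothing else in the plan returns the excluded subjects to the noise analysis. If the narrow meaning was intended, one sentence would settle it.

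A second reply is that no noise comparison between hearing groups is planned. This stands in part. The Design section limits the case-control comparison to MOCR measures, and the SAP links noise only to unlisted testing factors. A reader might infer that the rule must hide a noise difference between normal-hearing and hearing-loss subjects, because one cut-off removes more of the noisier group. The documents do not support that: they state no such comparison, and with unequal spreads the cut-off can remove more of the quieter group and widen the difference.

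A third reply is that a within-subject contrast is safe. That is so if exclusion uses the subject's average noise. The SAP does not say what is used, and other choices bias the contrast downward or upward.

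The fall in mean noise depends on neither of the last two replies.

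**Conclusion.** The point holds as a defect of scope. As written, the exclusion selects on an analysed outcome. If anyone is excluded on a judgement positively related to measured noise, mean noise is understated; under the normal illustration the fall is about 0.1 to 0.35 SD for 5 to 20% removed, and less if the relation is loose. The actual size cannot be computed from the documents, and it is zero if nobody was excluded.

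The effect on contrasts is conditional on which ones are tested, and it has no fixed direction. The point does not show that the comparison of MOCR measures is biased. It deserves correction because the change is specific and cheap and can alter a reported result. Confidence is medium, since the intended scope of the rule is not stated.

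**What to change.** State in the SAP that the noise exclusion applies to the MOCR-strength analysis only. Analyse noise, sweeps and test time on all tested subjects with recorded values, and state how many lack them.

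The cost is a sentence or two of SAP text and a small re-analysis of recordings already made. It depends on noise, sweep and time values having been kept for the excluded subjects. The downside is that reported noise may look less favourable.
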